13.5.3. Safety Endpoint

- Incidence of treatment-emergent adverse events (TEAEs) and serious adverse events (SAEs), grouped by organ system, relatedness to study medication, and severity
- Percentage of subjects whose IOP increases are > 10 mmHg from their own Parent study baseline measurement at each follow-up visit
- Percentage of subjects whose IOP increases to a reading > 30 mmHg at each follow-up visit
- Percentage of subjects who require 1 or more additional IOP lowering medications at any follow-up visit

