9.2.2. Additional Treatment

If at any time during the study a subject is considered at immediate risk for a vision-threatening event, the Investigator should immediately follow best medical practice in the Investigator's judgment for treating the subject. All additional therapy will be recorded in the subject's medical chart and the CRF.

Rescue Criteria

If at any time during the study any of the following criteria are met in the study eye, the use of a treatment should be introduced. The therapy implemented is left to the discretion of the Investigator.

- A loss of 10 or more ETDRS BCVA letters due to uveitis from either of the previous two visits
- CSF > 320 μ m OR an increase in CST of \geq 100 microns or 20%, whichever is lower, from either of the previous two visits
- In the investigator's medical judgement, the uveitic complications in the study eye have worsened and the condition needs to be addressed

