9.3. Treatment Compliance

Once a subject has been treated with additional therapy, the subject should be exited from the study per the Schedule of Assessments ([Section 20.1 - Appendix A](#)).

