12.4. Recording Adverse Events

Adverse events spontaneously reported by the patient/subject and/or in response to an open question from the study personnel or revealed by observation will be recorded during the study at the investigational site. The AE term should be reported in standard medical terminology when possible. For each AE, the investigator will evaluate and report the onset (date and time), resolution (date and time), intensity, causality, action taken, serious outcome (if applicable), and whether or not it caused the patient to discontinue the study.

The **intensity** of each AE will be graded using National Cancer Institute (NCI) Common Terminology Criteria for Adverse Events (CTCAE) v 4.03. The criteria can be accessed at: http://evs.nci.nih.gov/ftp1/CTCAE/CTCAE_4.03_2010-06-14_QuickReference_5x7.pdf.

The term “severe” is a measure of intensity. A severe AE is not necessarily a serious AE.

Grade refers to the severity of the AE. The CTCAE displays Grades 1 through 5 with unique clinical descriptions of severity for each AE based on this general guideline:

| | |
|---------|---|
| Grade 1 | Mild; asymptomatic or mild symptoms; clinical or diagnostic observations only; intervention not indicated |
| Grade 2 | Moderate; minimal, local or noninvasive intervention indicated; limiting age-appropriate instrumental activities of daily living (ADL) |
| Grade 3 | Severe or medically significant but not immediately life-threatening; hospitalization or prolongation of the hospitalization indicated; disabling; limiting self-care ADL |
| Grade 4 | Life threatening consequences; urgent intervention indicated |
| Grade 5 | Death related to AE |

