13.5. Analysis Methods

13.5.1. Primary Efficacy Endpoint

Time to rescue therapy (dosing with a drug when efficacy of the Parent study investigational products is no longer adequate)

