20. APPENDICES

20.1. Appendix A: Schedule of Assessments

| Assessment | Crossover ¹ | Extension Study Visit | | | | Early Termination |
|---|------------------------|-----------------------|---------|---------|---------|-------------------|
| | | Week 24 | Week 30 | Week 36 | Week 42 | |
| Parent Study | Week 24 | Week 30 | Week 36 | Week 42 | Week 48 | |
| Extension Study | Day 0 | Week 6 | Week 12 | Week 18 | Week 24 | |
| Informed Consent | X | | | | | |
| Inclusion/ Exclusion | X | | | | | |
| Assess AEs | X | X | X | X | X | X |
| Con Med Review | X | X | X | X | X | X |
| BCVA ² | X | X | X | X | X | X |
| Slit lamp Biomicroscopy ^{2,3} | X | X | X | X | X | X |
| IOP ² | X | X | X | X | X | X |
| Dilated Indirect Ophthalmoscopy ² | X | X | X | X | X | X |
| SD-OCT ² | X | X | X | X | X | X |

1 Same as parent study Week 24 visit. Ensure these procedures are completed. Do not repeat if done in parent study.

2 All ophthalmic assessments should be completed for the study eye only

3 Any finding of cataract should be graded

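### The IOP-treatment endpoint omits IOP-lowering laser and surgery, and the drug-only primary event conflicts with the plan's wider term, additional therapy

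*Combined protocol and SAP*

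**What the plan says.** **IOP endpoints.** Section 13.5.3 lists three. Two depend on readings: a rise of more than 10 mmHg from the subject's own Parent study baseline, and "Percentage of subjects whose IOP increases to a reading > 30 mmHg at each follow-up visit". The third depends on treatment and names drugs alone: "Percentage of subjects who require 1 or more additional IOP lowering medications at any follow-up visit".

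**Primary event.** Section 13.5.1 explains rescue as "dosing with a drug when efficacy of the Parent study investigational products is no longer adequate". The primary objective (Section 6.1) and the synopsis use a wider idea: additional uveitis therapy or a change in maintenance treatment, with no restriction to drugs.

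**What ends participation.** On rescue, Section 9.2.2 says "The therapy implemented is left to the discretion of the Investigator". Section 9.3 says "Once a subject has been treated with additional therapy, the subject should be exited from the study". The list in Section 9.2.1 is described as a guide rather than a complete list, and it includes investigational devices as well as investigational drugs.

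**What is collected.** Appendix A has a "Con Med Review" row at every visit and no row for procedures. It also has an adverse event row at every visit. Section 12.4 records, for each event, "intensity, causality, action taken, serious outcome (if applicable), and whether or not it caused the patient to discontinue the study". Section 9.2.2 sends all additional therapy to the chart and the CRF.

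**Analysis.** Section 13.5.2 specifies Kaplan-Meier estimates and a log-rank test between treatments. It gives no censoring rule.

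**The concern.** The two endpoints have different gaps.

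For IOP, a laser or surgical procedure to lower pressure is at least as strong a sign of a pressure problem as an added drop, yet the treatment-based endpoint does not see it. The secondary objective is the continued safety of a corticosteroid, so the IOP-treatment percentage would be understated.

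For the primary endpoint, the plan uses two definitions of failure. One decides who leaves the study (any additional therapy) and the other decides who has an event (a drug dose). A subject who falls between them leaves because treatment failed but has no event. If that subject is censored at exit, the censoring is informative: it removes a failure from the numerator and carries the more favourable experience of the remaining subjects forward in its place.

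**Working it through.** The plan states no event rate, power or allocation for the extension, so there is no figure of its own to reproduce. The check compares the definitions and then gives a sense of scale on assumed counts.

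**Step 1: who is counted where, read literally**

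| Study eye receives | Exits under 9.3 | Event under 13.5.1 | Additional therapy under 6.1 |
|--|--|--|--|
| Drug for uveitis, including an injection or implant | Yes | Yes | Yes |
| Investigational device or drug-free procedure for uveitis or its macular edema | Yes | No | Yes |

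The second row is the conflict. The device item in Section 9.2.1 shows that the protocol's own list reaches it.

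**Step 2: IOP endpoints.** Scheduled visits are 6 weeks apart (Section 7.1). Assume a rise of more than 10 mmHg found at an unscheduled visit, treated by laser with no new drug, and pressure near baseline at every scheduled visit. That eye meets neither reading-based endpoint, since both are evaluated at follow-up visits, and it does not meet the medication endpoint. Each such eye lowers the IOP-treatment percentage by 1/30 = 3.3 points.

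**Step 3: primary endpoint, small illustration (assumed).** One arm of 20, one drug rescue at each of Weeks 6, 12 and 18, and one eye treated by a procedure at Week 12.

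- Procedure censored at exit: 19/20 × 18/19 × 16/17 = 84.7% rescue-free at Week 24.
- Procedure counted: 19/20 × 17/19 × 16/17 = 80.0%.
- Difference: 4.7 points.

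**Step 4: larger illustration (assumed).** All 30 subjects in one curve, 12 treated eyes, 3 at each of Weeks 6, 12, 18 and 24. Of these, k are treated without a drug, one at each of the first k visits. The estimate is the product over visits of (1 − events/at risk). With k = 0 it is 27/30 × 24/27 × 21/24 × 18/21 = 60.0%. With k = 1, censored at exit, it is 28/30 × 24/27 × 21/24 × 18/21 = 62.2%.

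| k | All therapy counted | Non-drug eyes censored at exit | Non-drug eyes kept event-free to Week 24, 1 − (12 − k)/30 |
|--|--|--|--|
| 1 | 60.0% | 62.2% | 63.3% |
| 2 | 60.0% | 64.8% | 66.7% |
| 3 | 60.0% | 67.9% | 70.0% |
| 4 | 60.0% | 71.7% | 73.3% |

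Within one curve the direction is always upward. Only the size depends on the assumed counts.

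**The case against.** The strongest reply has four parts.

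- **The data are not lost.** Under Section 12.2.1.1 a clinically significant ophthalmic finding that needs specific treatment can be an adverse event, and under Section 12.2.1.2 an important event that may need surgery can be serious. Action taken is recorded and additional therapy goes on the CRF. This stands. A reader might infer from the medication row in Appendix A that procedures go unrecorded, but the documents do not support that. What remains is narrower: no IOP endpoint counts a procedure, and the schedule does not prompt for one.
- **The primary event is not settled as drug-only.** The objective and synopsis are wider, and Section 13 leaves data-handling conventions to a separate analysis plan. This also stands, and it makes the point one of internal conflict. A reader might go further and say that a procedure-treated eye is scored as event-free to Week 24. The documents do not say so. Given the exit rule, censoring at exit is the more natural literal reading, and no censoring rule confirms even that.
- **Procedures that deliver a drug are covered.** Injections and implants are drug dosing and appear in Section 9.2.1. Only non-drug therapy falls in the gap.
- **The bias need not favour CLS-TA.** A reader might infer that the error always flatters the product. That is true of a single arm's curve. In the log-rank comparison, an uncounted failure in the sham arm would work against CLS-TA.

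The reply also notes, correctly, that no frequency is given and that the IOP example needs several circumstances together. That limits the importance of the gap but does not close it.

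**Conclusion.** The point holds in two parts. The IOP-treatment endpoint omits IOP-lowering laser and surgery, which may leave such an eye outside all three IOP endpoints while still visible as an adverse event. The primary event in Section 13.5.1 conflicts with Sections 6.1, 9.2.1, 9.2.2 and 9.3 and with the synopsis on whether non-drug therapy counts, and no stated rule resolves the conflict.

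The size is 3.3 points per uncounted eye on a percentage of 30. On the primary curve it is about 2 to 12 points for one to four censored eyes among 12 treated (62.2% to 71.7% against 60.0%), or 4.7 points for one eye in an assumed arm of 20. These rest on assumed counts and on censoring at exit. The true frequency is not stated and is probably low, so this is a definition to tidy before the analysis plan is final rather than a threat to the study.

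**What to change.** 1. **Section 13.5.3, fourth bullet.** After the reference to added medications, insert: *or an IOP-lowering laser or surgical procedure in the study eye*.
2. **Section 13.5.1.** Replace the drug-dosing gloss with: *first additional therapy for uveitis or its macular edema, drug or non-drug, or increase in maintenance therapy, that counts as additional therapy for the study eye under Sections 9.1.2, 9.2.1 and 9.2.2, including systemic therapy*. State that an exit for such therapy is an event and is not censored. The reference to those sections is needed because wording limited to treatment given in the study eye could drop the systemic therapies that Sections 9.1.2 and 9.2.1 already count.
3. **Appendix A.** Record ocular procedures alongside the medication review.

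These changes alter what is counted and recorded, not how any subject is managed. The cost is two endpoint sentences and one extra CRF line. The downside for the sponsor is that the rescue and IOP-treatment percentages may become slightly less favourable.

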13.5.4. Safety Analysis

13.5.4.1. Intraocular Pressure

The observed and change from baseline in IOP will be summarized descriptively at each visit. Descriptive statistics include n, mean, median, minimum and maximum values.

13.5.4.2. Cataract Lens Grading

The distribution of responses (n, %) will be tabulated for each category of response.

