5. INTRODUCTION

5.1 Disease Background

Uveitis is the fifth most common cause of visual loss in the developed world ([Goldstein 2009](#); [Wood 2011](#); [Miserocchi 2013](#)). Significant vision loss can occur in up to 35% of children and adults, and uveitis accounts for 5% - 20% of legal blindness in both the United States and Europe, and perhaps as much as 25% of blindness in the developing world ([Rothova 1996](#); [Bodaghi 2001](#)).

There are a number of causes associated with this vision loss including cataract formation or progression, chorioretinal scarring, retinal detachment, and secondary glaucoma, but the dominant cause of vision loss within uveitis comes from chronic macular edema accounting for about one third of visual impairment or blindness ([Wood, 2011](#); [Dick, 1994](#); [Karim, 2013](#)). Approximately 30% of all uveitis patients and up to 60% of intermediate- and pan-uveitis patients experience macular edema ([Lardenoye, 2006](#)).

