12.1.2. Slit-Lamp Biomicroscopy

Slit-lamp biomicroscopy, including magnification, will be performed at every visit and consistent with standard clinical practice. This procedure should be conducted in the same manner for all subjects and will include an assessment of each of the following as normal or abnormal: eyelids, cornea, anterior chamber, iris and lens. All abnormal findings will be described.

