12.1.2.1. Cataract Lens Grading

If an abnormal finding of cataract is noted for the lens during the slit-lamp exam, the cataract should be assessed for nuclear opalescence, cortical opacity and posterior subcapsular opacity. Graders must verify training on the grading procedure provided in the Manual of Procedures.

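### Cataract grades are summarised only as a distribution with no stated denominator, so the plan specifies no grade-based rate of new or worsened cataract by Parent arm

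*Combined protocol and SAP*

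**What the plan says.** Section 12.1.2.1, under the safety parameters, makes grading conditional: "If an abnormal finding of cataract is noted for the lens during the slit-lamp exam, the cataract should be assessed for nuclear opalescence, cortical opacity", with posterior subcapsular opacity as the third component. Footnote 3 of the Schedule of Assessments (Appendix A) agrees: "Any finding of cataract should be graded". Section 12.1.2 requires a slit-lamp examination at every visit, which "will include an assessment of each of the following as normal or abnormal: eyelids, cornea, anterior chamber, iris and lens".

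Section 13.5.4.2 then plans one thing for the grades: "The distribution of responses (n, %) will be tabulated for each category of response". It names no visit, arm, denominator or baseline.

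IOP is treated differently. Section 13.5.4.1 states "The observed and change from baseline in IOP will be summarized descriptively at each visit", and Section 13.5.3 adds three IOP endpoints, the last being "Percentage of subjects who require 1 or more additional IOP lowering medications at any follow-up visit". Section 13.5.3 has no cataract endpoint.

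**The concern.** The clinical question about the lens is a within-eye one: did this eye develop a cataract, or did an existing one get worse? A marginal distribution of grades does not answer it. Because only eyes with a visible cataract carry a grade, the set of graded eyes changes as cataracts appear. Because subjects leave the study after additional therapy (Sections 9.2.1 and 9.3), the set also shrinks over follow-up. Two visit tables may then describe different eyes.

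The secondary objective concerns maintained safety, and Section 5.1 treats the lens as relevant to this population: "There are a number of causes associated with this vision loss including cataract formation or progression". As written, the report could contain a full cataract table for each arm without the proportion of study eyes with new or worsened cataract. With no denominator stated, the percentages could also be produced in a form that moves the wrong way.

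**Working it through.** The documents give no cataract rate, so there is no figure to reproduce. All cataract counts below are assumptions, used only to show how the planned table behaves. "Low" and "high" stand for grades of any one component, because the scale itself is in the Manual of Procedures.

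**1. Percentages of graded eyes.** Assume 15 study eyes in an arm (about 30 subjects, split evenly), with 4 high-grade cataracts at Crossover and 4 new low-grade cataracts by Week 24.
- High-grade share of graded eyes: 4/4 = 100% at Crossover; 4/(4 + 4) = 4/8 = 50% at Week 24.
- Eyes with any cataract: 4/15 = 26.7%, then 8/15 = 53.3%.

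**2. A less extreme start.** Assume 30 eyes pooled, of which 10 are graded at Crossover (4 mild, 4 moderate, 2 severe). The moderate-or-severe share is 6/10 = 60.0%.

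| Change by Week 24 | Share of graded eyes | Eyes new or worse |
|---|---|---|
| 2 new mild | 6/12 = 50.0% | 2/30 = 6.7% |
| 4 new mild | 6/14 = 42.9% | 4/30 = 13.3% |
| 6 new mild | 6/16 = 37.5% | 6/30 = 20.0% |
| 4 new mild, and 1 mild becomes moderate | 7/14 = 50.0% | 5/30 = 16.7% |

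In the last row an existing cataract worsened and the share still fell from 60.0% to 50.0%.

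**3. The same data over all eyes.** With 4 new mild cataracts, moderate or severe stays at 6/30 = 20.0% and any cataract rises from 10/30 = 33.3% to 14/30 = 46.7%. The apparent improvement disappears.

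**4. What remains with the better denominator.** Suppose one eye goes from low to high and another eye's high-grade lens is removed. The high-grade count changes by +1 − 1 = 0. The high-grade row does not move although one eye worsened and another had lens surgery. Only a cross-tabulation of each eye's Crossover grade against its later grade shows this.

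**5. Precision of a progression proportion.** With no events, the exact upper 95% limit is 1 − 0.025^(1/n).
- n = 30: 11.6%. n = 15: 21.8%.
- 4/30 = 13.3%, exact 95% CI 3.8% to 30.7%. 4/15 = 26.7%, exact 95% CI 7.8% to 55.1%.
- At an assumed true rate of 5%, the chance of at least one event is 1 − 0.95^30 = 78.5% for n = 30 and 1 − 0.95^15 = 53.7% for n = 15.

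**The case against.** A reader might infer that the planned table will make cataract look better as new cases appear. The documents do not support that. Section 13.5.4.2 does not say that percentages are of graded eyes, and Section 13.4.1 assigns safety analyses to the Safety Population, which points to all subjects who complete Crossover. The table also reports n: in the first example a reader would see 4 graded eyes become 8. The reversal is a risk left open by an unstated denominator, not a consequence of following the plan.

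A reader might also infer that no information on progression will be obtained. That is too strong. There are three partial routes:
- **Adverse events (Section 13.5.4.5).** Incidence is summarised by preferred term, and worsening of a pre-existing condition after Day 0 counts. But a lens finding enters only if reported as an AE. Section 12.2.1.1 leaves the significance of ophthalmic findings to the investigator and leaves out expected signs of the disease. The table may be replaced by a listing if few events are reported.
- **Lens normal/abnormal (Sections 12.1.2 and 13.5.4.3).** This is tabulated and covers ungraded eyes, but cannot show an existing cataract getting worse.
- **Listings (Section 13.5.2).** Change from Crossover is listed, and with about 30 subjects it could be counted by hand. It is not a planned rate by arm.

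Further points stand. Section 13 promises a detailed SAP that could settle the denominator and add a shift table. The documents name cataract as a cause of vision loss in uveitis and do not attribute it to the product. No cataract endpoint is claimed, the study is descriptive, and the first illustration is deliberately extreme. These limit the weight of the point. They do not supply the missing summary.

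**Conclusion.** The point holds in limited form. The only summary specified for cataract grades is a marginal count and percentage with no stated denominator. It yields no grade-based rate of new or worsened cataract by Parent arm, whichever denominator is used. This conclusion rests on the text alone.

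The misleading direction of the percentages is conditional on using graded eyes. Under the assumed counts it ranges from 100% falling to 50% in the extreme case to 60.0% falling to 42.9% in the milder case with 4 new mild cataracts. It is absent with all eyes as denominator.

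The primary analysis is not affected. This is an inexpensive improvement to a safety summary, built on examinations already scheduled at every visit. With about 30 subjects the resulting rates will be imprecise and should be read as description.

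**What to change.** In Section 13.5.4.2 and in the detailed SAP, replace the marginal table, or supplement it, with the following:

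- **Denominator:** all Safety Population study eyes with a natural lens at Crossover, with lens status taken from the slit-lamp description.
- **Scoring:** no cataract counts as grade 0, separately for nuclear, cortical and posterior subcapsular components.
- **Summary by Parent arm:** a shift table from the Crossover grade to the worst post-Crossover grade, including the Early Termination visit.
- **Rate by Parent arm:** n (%) of eyes with new cataract or any increase in a component grade, with exact (Clopper-Pearson) 95% confidence intervals.
- **Lens removal during follow-up:** a category of its own, so that such an eye does not appear as unchanged or improved.
- **Parent baseline:** add the shift from Parent baseline only if that grade was recorded there.

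The cost is SAP wording and one extra table, with no new examination. One item needs checking first: Section 12.1.2 asks for normal or abnormal and a description of abnormal findings, but does not name lens status as a field. The sponsor should confirm that it can be derived.

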13.5.4.3. Slit-Lamp Biomicroscopy

The distribution of responses (n, %) will be tabulated for each category of response.

13.5.4.4. Dilated Indirect Ophthalmoscopy

The distribution of responses (n, %) will be tabulated for each category of response.

